5.4. Assignment / randomization (if applicable)

After eligibility is confirmed in REDCap, participants will be registered in the CTMS system. Upon completion of baseline assessment, participants will be randomized using the REDCap randomization module to one of the two arms (i.e., LungTalk or non-tailored GO² video) using a stratified block design stratifying by smoking status (current vs former). Stratified random assignment will ensure the two groups are comparable in distribution on smoking status, a salient variable for lung screening behavior noted in our prior work.^{9,17,41} Consolidated Reporting of Randomized Clinical Trials (CONSORT) guidelines for RCTs will be followed.

5.5. Section of instruments (to include for all studies with a social behavioral intervention)

Table 1. Measures and Timepoints of Assessment

Constructs	Assessment or Measure	# of Items	Time to Complete (min)	Validated?	Baseline (T1)	1 Wk Follow-Up (T2)
Eligibility	Screening Survey	3	1	N		
Demographics	Demographic and Health Status Characteristics	20	5	N	X	
Knowledge	Knowledge: Lung Cancer Screening	9	5	N	X	X
Perceived Risk	Perceived Risk of Lung Cancer Scale ¹⁶	3	1	Y	X	X
Perceived Benefits	Perceived Benefits of Lung Cancer Screening Scale ¹⁶	6	3	Y	X	X
Perceived Barriers	Perceived Barriers to Lung Cancer Screening Scale ¹⁶	17	10	Y	X	X
Self-Efficacy	Self-Efficacy for Lung Cancer Screening Scale ¹⁶	9	5	Y	X	X
Occurrence of a Patient-Clinician Discussion	Self-report of Occurrence of a Patient-Clinician Discussion about Lung Cancer Screening	1	1	N	X	X
Screening Uptake	Self-report via the stages of adoption algorithm for screening with verification process	1	1	N	X	X
Upcoming PCP Visit	Self-report of upcoming visit with	1	1	N	X	X

	primary care provider scheduled				
1. Screening Survey	TOTAL TIME		32 minutes	27 minutes	

will be used to determine eligibility. See Section 4.3.b above for details.

2. **Demographic and Health Status Characteristics** will be assessed using items we have used in prior studies. These include age, gender, race/ethnicity, education level, income level, perceived financial status, insurance status, marital status, employment status, smoking status (if former, how long since quit in months), and family history of lung cancer.

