6. **Lung Cancer Screening Uptake** is the primary outcome and will be assessed via self-report via the stages of adoption algorithm for lung screening. The algorithm for collecting this item presents additional questions conditional on responses (see Appendix D). There are seven stages (*unaware, aware but unengaged, undecided, decided not to act, decided to act, action, and maintenance*). This will help to understand screening behavior more robustly by understanding the stages of decision-making and adoption (i.e., uptake) of the behavior. Please note that screening uptake is considered stages 6 and 7 (action and maintenance).

The description of lung cancer screening with LDCT of the chest developed in our preliminary studies includes a picture and a written description of an LDCT. This description is embedded in the follow up surveys (Appendix C) prior to the self-reported question to ensure participants understand the question. Using the same successful procedure as in our prior pilot RCT for LungTalk,⁴⁵ we will verify screening for individuals who self-report completing an LDCT of the chest to screen for lung cancer by mailing an authorization form to be signed and mailed back to the research office. Trained research staff will verify the screening LDCT scan using the information and signed authorization form by contacting the facility directly to request confirmation.

7. **Upcoming Primary Care Provider Visit** will be measured with one item: Do you have an appointment already scheduled to follow-up with your primary care provider? If yes, when?

In order to generate a robust semi-structured interview guide about the sustainability of a social media-based approach to increasing lung screening awareness and uptake, key stakeholder participants representing administrators (healthcare system and screening centers), key screening center personnel, advocacy organizations (i.e., LUNGevity, Dusty Joy Foundation), and national organizations (American Cancer Society, American Lung Association, GO₂ Foundation for Lung Cancer) will be conducted. We will begin the Key Stakeholder participant recruitment no earlier than Year 3 of the study. These stakeholder participants will complete one semi-structured interview that will take 45-60 minutes to complete. We will amend the protocol to include the semi-structured interview guide that will be informed and created from the quantitative data collected from the participants.

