5.7. Follow-up and end-of study (if applicable) n/a

5.8. Statistical Method

This behavioral intervention study will randomize 500 screening-eligible individuals in a 1:1 ratio into the *LungTalk* intervention or the non-tailored video intervention condition. We will use descriptive statistics such as means, standard deviations, and frequency distributions/distributional assumptions to examine data quality, identify patterns of missing and out-of-range values, and evaluate parametric assumptions. Remediation of normal distribution assumption violations will be accomplished using the Box-Cox procedure for transformations. We will apply the intention-to-treat (ITT) principle in handling missing data on screening uptake; a study participant will be coded as 'no screening uptake' unless otherwise verified by our participation sites. We will examine violations of the missing-at-random assumption for secondary outcomes. If missingness is associated with any

observed characteristics, then covariates associated with missingness will be incorporated into a sensitivity analysis to minimize bias.

Aim 1. Examine the use of a social media platform (i.e., Facebook) to reach high-risk individuals eligible for lung screening. We will describe and compare the following measures and metrics using a mixture of data from FB analytics and study data from REDCap.

Goal	Analytic Plan
Estimate the number and percentage of individuals aged 50 and older who currently or formerly smoke in the population that the advertisement is marketed.	Numerator = # of Facebook members age 50+ who currently or formerly smoke in target markets Denominator = total # of Facebook members in target markets Both numerator and denominator provided by FB Analytics.
Estimate the approximate percent of this population to which this advertisement is marketed are eligible for lung screening according to the USPSTF guidelines.	Numerator = # of eligible participants, among those screened. Denominator = total number screened. Data from screening survey.
Record the percent of eligible participants who agree to participate in the study.	Numerator = total number consented Denominator = # of eligible participants
Compare differences between those participating and those not participating on smoking status (i.e., current vs. former), age, gender, geography, and other key variables collected on the screening survey.	Descriptive tables along with a series of independent samples t-tests and Chi-square tests.

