Record reasons that participants refuse to participate in the study.	Descriptive analysis from screening survey data.
Estimate attrition at 1 week and 6-month follow-up time periods.	Numerator = # of baseline participants - # of participants who complete the follow-up assessment (either 1 week or 6 month) Denominator = # of baseline participants Completion at follow-up defined as completing, at the least, the screening/stage of adoption item.
Compare differences between those completing and those not completing the study on sociodemographic and health status variables, geography, baseline scores on knowledge, lung cancer screening health beliefs, and stage of adoption for lung cancer screening.	Descriptive tables along with a series of independent samples t-tests and Chi-square tests. Completion of the study is defined as completing the screening uptake item for the 6-month assessment.

Aim 2. Compare the effectiveness of a computer-tailored health communication and decision support tool (LungTalk) to a non-tailored Lung Screening Informational Video on lung screening: 1)

knowledge; 2) health beliefs (perceived risk, perceived benefits, perceived barriers, self-efficacy); 3) occurrence of a patient-clinician discussion about lung screening; and 4) uptake and completion (primary outcome). Total knowledge scale scores and Lung Cancer Screening Health Beliefs (total scale scores for perceived risk, perceived benefits, perceived barriers, self-efficacy) are continuous variables. Occurrence of patient-clinician discussion and screening uptake are dichotomous variables. Prior to group comparisons, measures will be described by timepoint, both overall and by group. Within-group changes will be assessed using standardized effect sizes. The primary outcome is screening uptake at 6-month follow-up. For between-group comparisons, generalized linear models will be used with adjustment for smoking status; appropriate link functions for each outcome will be determined based on distributions (e.g., for dichotomous outcome variables we will use a logit link). In the case of differential attrition, as noted above, a sensitivity analysis will be conducted such that regression models will also include baseline covariates that differ significantly between participants who do and do not complete follow-up assessments.

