5.8.2. Statistical Analysis Plan

With a sample size of n=250 per intervention group, and using an ITT analysis (default is no screening uptake unless otherwise verified, thus no "missing" outcome data), we will be able to detect a difference between the *LungTalk* and non-tailored educational video groups with an 80% statistical power if the difference in lung screening uptake at 6-month follow-up (primary outcome) is 25% in the *LungTalk* group compared to 15% in the non-tailored educational video groups, in a test of independent proportions and a two-sided type-I error rate of 5%. This 25% vs. 15% comparison is a conservative estimate, as 31% vs. 10% difference was observed in preliminary data testing *LungTalk* in a sample of community-based screening-eligible individuals in Indiana in 2018 using the same ITT procedure.¹⁶

6 - Trial Administration

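### The primary uptake model is valid at its stated 80% power, but it leaves out three plausible predictors measured before randomisation; pre-specifying them costs little and gains roughly 0 to 6 points of power

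*Combined protocol and SAP*

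**What the plan says.** Section 5.8 (Aim 2) defines the primary endpoint: "The primary outcome is screening uptake at 6-month follow-up". For all between-group comparisons "generalized linear models will be used with adjustment for smoking status", and "for dichotomous outcome variables we will use a logit link". Smoking status is also the randomisation stratum (Section 5.4).

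One other route brings baseline variables into these models. If attrition is differential, a sensitivity analysis is run in which "regression models will also include baseline covariates that differ significantly between participants who do and do not complete follow-up assessments".

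The baseline (T1) assessments in Section 4.3.c and Table 1 of Section 5.5 include stage of adoption, whether a patient-clinician discussion has occurred, and an upcoming visit. The visit item asks "Do you have an appointment already scheduled to follow-up with your primary care provider", and if so when (Section 5.5, item 7). All three precede allocation: "Upon completion of baseline assessment, participants will be randomized using the REDCap randomization module" (Section 5.4).

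The trial "will randomize 500 screening-eligible individuals in a 1:1 ratio" (Section 5.8). Section 5.8.2 sizes the primary comparison with an unadjusted test of two proportions, 25% versus 15%, two-sided 5%, 80% power, and missing or unverified uptake counted as no uptake.

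**The concern.** The documents themselves make the three baseline items plausible predictors of uptake. Section 2.1.a says reimbursed screening requires a shared decision-making visit. Section 4.3.c places the clinician discussion before referral. In the adoption algorithm (Section 5.5, item 6), deciding to act is the stage immediately before action, and action counts as uptake.

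Adjusting a randomised comparison for pre-specified baseline predictors keeps the test valid and, in a logit model, usually raises power. The attrition-triggered sensitivity analysis does not serve this purpose: it selects variables because they relate to completion, not because they predict uptake. What is at stake is some efficiency, not validity.

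The discussion outcome has a more specific problem. Its item (Section 5.5, item 5) asks whether a discussion has ever taken place, with no time window. Someone who truthfully says yes at baseline will say yes at follow-up in either arm. Ignoring the baseline answer therefore dilutes any effect.

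**Working it through.** **1. The plan's own figure.** Inputs from Sections 5.8 and 5.8.2: 250 per arm, 25% versus 15%, two-sided 5%.

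- Null SE = √(2 × 0.20 × 0.80 / 250) = 0.0358.
- Alternative SE = √((0.25 × 0.75 + 0.15 × 0.85) / 250) = 0.0355.
- Power = Φ[(0.10 − 1.96 × 0.0358) / 0.0355] = 80.0%.

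The required size from the same formula is 250 per arm, so the stated figure reproduces.

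**2. Gain by formula.** Let R² be the share of outcome variance explained by the added covariates. The documents do not give it, so it is an assumption. Multiplying both variances by (1 − R²):

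| R² | Power |
|---|---|
| 0 | 80.0% |
| 0.02 | 80.8% |
| 0.05 | 82.0% |
| 0.10 | 84.0% |
| 0.15 | about 86% |

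Equivalently, R² = 0.05 lowers the size needed for 80% power to 250 × 0.95 = 237.5, or 238 per arm; R² = 0.10 lowers it to 250 × 0.90 = 225.

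**3. Simulation, three covariates.** 500 participants, 4,000 replicates, allocation stratified by smoking, marginal uptake held at 25% and 15%. Assumed: 50% current smokers, 40% with a visit, 20% with a prior discussion, baseline stage spread over five stages.

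| Odds ratios (visit, discussion, per stage) | R² | Smoking only | Adjusted | Gain |
|---|---|---|---|---|
| 1, 1, 1 | 0 | 80.6% | 80.4% | −0.2 |
| 1.5, 1.5, 1.2 | 0.02 | 79.7% | 80.3% | 0.6 |
| 2, 2, 1.5 | 0.06 | 79.2% | 81.9% | 2.6 |
| 3, 3, 2 | 0.15 | 79.7% | 85.5% | 5.8 |

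Gains are taken before rounding. Monte Carlo error is about 0.6 points per power estimate. Type I error was 4.6% to 5.3% in both models.

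**4. Simulation, two covariates** (visit and decided to act, with the same odds ratio for each). Gains in points:

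| Odds ratio | 40% with a visit, 20% decided to act | Few decided to act |
|---|---|---|
| 1.5 | about 0 | about 0 |
| 2 | 1 | 0.4 |
| 3 | 4 | 2 |
| 4 | 5 | 3 |
| 5 | 6.5 | 4.5 |

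**5. Effect measure.** Uptake of 25% versus 15% is a marginal odds ratio of (0.25/0.75) / (0.15/0.85) = 1.89. In the step 3 scenarios with prognostic covariates, the adjusted (conditional) odds ratio is 1.91 to 2.12 for the same marginal rates.

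**6. Number of events.** Expected uptake is 500 × 0.20 = 100 events, enough for a handful of model terms.

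**7. Discussion outcome.** Illustration with assumed values: 20% say yes at baseline, new discussions occur in 35% versus 25% of the rest, and no data are missing.

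- All participants: 0.20 + 0.80 × 0.35 = 48% versus 0.20 + 0.80 × 0.25 = 40%. With 250 per arm, power is 44%.
- Baseline-no participants: 35% versus 25%. With 250 × 0.80 = 200 per arm, power is 59%.

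With 10% to 30% saying yes at baseline, the loss from ignoring the baseline answer is about 9 to 19 points.

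**The case against.** A reader might infer that the primary analysis is wrong or underpowered. The documents do not support that. Adjusting for the stratification factor is a valid pre-specified analysis, and it delivers the stated 80%.

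A reader might also say that the design has no power to spare. Section 5.8.2 calls 25% versus 15% conservative and cites 31% versus 10% from preliminary data; at those rates, 250 per arm gives power above 99.9%. The preliminary result may be optimistic, but the 80% applies at a deliberately cautious effect.

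Nor is it right that the three items can enter no model. Section 5.8 compares completers with non-completers on baseline stage, among other variables, and lets differing covariates into the sensitivity regressions. That route is conditional and built for attrition, but it exists.

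The size of the gain is open to challenge, and this part of the objection stands. No prevalence or odds ratio is given for any of the items. Section 1 describes eligible people as generally unaware of early detection, and the exclusion criteria (numbered 6.2) remove people with a prior LDCT. Baseline stage should therefore stop at decided to act, and that group may be small. Coding unverified uptake as none also weakens any covariate-outcome link. Large odds ratios are possible but not established.

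Chance imbalance is a weak argument too. With 40% having a visit, one standard deviation of imbalance is √(2 × 0.4 × 0.6 / 250) = 4.4 points. At an odds ratio of 3 that moves the unadjusted difference by about 0.6 points, roughly one-sixth of its standard error (0.6 / 3.55), and the test already allows for it.

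**Conclusion.** The point holds as a missed efficiency gain, not an error. The omission and the direction of the effect are clear from the text; the size rests on assumption. In the two-covariate setting the gain is about 0 to 1 points at odds ratios of 1.5 to 2, 2 to 4 at 3, and up to about 6 at 4 to 5. Three moderate predictors acting together (odds ratios 2, 2 and 1.5 per stage) give about 2.6. If the items do not predict uptake, there is no gain and no material loss. Type I error stays near 5% throughout.

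The discussion outcome is the firmer part. The carry-over of a baseline yes follows from the wording of the item, although the 9-to-19-point loss depends on the assumed rates.

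**What to change.** Before outcome data are seen, amend Section 5.8 (Aim 2):

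- **Primary model.** Logit of uptake on arm, smoking status, baseline upcoming visit (yes/no), baseline stage of adoption with a stated grouping, and baseline discussion (yes/no). One workable grouping is decided to act versus earlier stages.
- **Visit item.** State how the collected appointment date is used, since a visit beyond six months is unlikely to predict the outcome.
- **Effect measure.** Report the standardised risk difference with a 95% confidence interval by a named method, such as the delta method or bootstrap. This matches the scale on which the trial was sized.
- **Supporting analysis.** Keep the smoking-only model.
- **Discussion outcome.** Adjust for the baseline answer. If a baseline yes predicts follow-up perfectly, that coefficient cannot be estimated; analyse baseline-no participants instead. That subgroup is defined before randomisation, so the comparison stays randomised.

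The cost is a few sentences and no new data. Covariates and grouping must be fixed in advance, the adjusted odds ratio is conditional and must be labelled so, and the gain may be negligible if the predictors are weak.

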5.8.1. Sample size calculation and justification

With a sample size of n=250 per group and up to 20% missing assessment data (n=200 available for analysis) on total knowledge scale and total perceived risk scale scores (secondary outcomes), we will have an 80% statistical power if the difference is d=0.28 (in standardized effect size units, or Cohen d), in an independent-sample t-test with a two-sided type-I error rate of 5%. A 0.25 effect is what Cohen considered a 'small' effect size in psychology research, thus a conservative estimate of the statistical evidence that can be supported in our study design.

5.8.2. Statistical Analysis Plan

With a sample size of n=250 per intervention group, and using an ITT analysis (default is no screening uptake unless otherwise verified, thus no "missing" outcome data), we will be able to detect a difference between the *LungTalk* and non-tailored educational video groups with an 80% statistical power if the difference in lung screening uptake at 6-month follow-up (primary outcome) is 25% in the *LungTalk* group compared to 15% in the non-tailored educational video groups, in a test of independent proportions and a two-sided type-I error rate of 5%. This 25% vs. 15% comparison is a conservative estimate, as 31% vs. 10% difference was observed in preliminary data testing *LungTalk* in a sample of community-based screening-eligible individuals in Indiana in 2018 using the same ITT procedure.¹⁶

6 - Trial Administration

6.1. Ethical Considerations - Institutional Review Board (IRB) Review

The study will be conducted according to the International Conference on Harmonization (ICH), Good Clinical Practice (GCP), the Declaration of Helsinki, Institutional Review Boards (IRB) and in accordance with the U.S. Code of Federal Regulations on Protection of Human Rights (21 CFR 50).

6.2. Institutional Review Board (IRB) Review (list the IRB of record)

Hackensack Meridian Health

6.3. Confidentiality

HMH may allow the use and disclosure of protected health information pursuant to a completed and signed Research Authorization form. The use and disclosure of protected health information will be limited to the individuals/entities described in the Research Authorization form. A Research Authorization form must be approved by the IRB.

The consent indicates that individualized, de-identified information collected for the purposes of this study may be shared with other qualified researchers. Only researchers who have received approval from HMH will be allowed to access this information, which will not include protected health information such as the participant's name, except for dates.

6.4. Informed consent

All participants (N=500) (except stakeholders) will sign an e-consent in REDCap.

The consent form/research authorization meets the requirements of the Code of Federal Regulations and the Institutional Review Board/Privacy Board of HMH. The consent form will include the following:

1. The nature, objectives, potential risks, and benefits of the intended study.
2. The length of study, what it entails, and the likely follow-up required.
3. Alternatives to the proposed study.
4. The name of the investigator(s) responsible for the protocol.
5. The right of the participant to accept or refuse study interventions/interactions and to withdraw from participation at any time.
6. How the participants' data will be protected, who will have access to their PHI, and what data will be disclosed for research purposes.

Prior to inclusion in the study and before protocol-specified procedures are carried out, potential participants will be able to read the full details of the protocol as outlined in the consent and research authorization. Participants will have the ability to contact the investigator if there are any questions prior to consenting electronically. Participants will also be informed that they are free to withdraw from the study at any time.

All participants must electronically sign an IRB-approved consent form via REDCap indicating their consent to participate. A consenting professional signature is not required as noted in IRB SOP IC-706. The participant will be offered to receive a copy of the signed informed consent form either by email or by mail.

Key stakeholder participants (N=20) will be consented over the phone using a verbal consent.

The verbal informed consent/research authorization meets the requirements of the Code of Federal Regulations and the Institutional Review Board/Privacy Board of HMH. The consent/research authorization script will include the following:

1. The nature, objectives, potential risks, and benefits of the intended study.
2. The length of study, what it entails, and the likely follow-up required.
3. Alternatives to the proposed study.
4. The name of the investigator(s) responsible for the protocol.
5. The right of the participant to accept or refuse study interventions/interactions and to withdraw from participation at any time.
6. How the participants' data will be protected, who will have access to their PHI, and what data will be disclosed for research purposes.

Prior to inclusion in the study and before protocol-specified procedures are carried out, consenting professionals will explain the details of the protocol to participants. Participants

will also be informed that they are free to withdraw from the study at any time. The consent discussion will occur remotely via teleconference, telephone, or videoconference.

